**Low Intensity Focused Ultrasound of Medial Temporal Lobe
Regions for the Improvement of Learning and Memory /
Low Intensity Focused Ultrasound as a Non-Invasive Neural
Prosthetic for the Improvement of Emotion Regulation**

NCT03717922
Document Date: 12/8/2023

APPROACH

Participants. Participants will consist of 21 adults aged 35-90

Subject Recruitment. Participants will be recruited from the Human Connectome Project – Aging participant pool and through fliers placed around campus and greater Los Angeles.

Eligibility. Inclusion criteria: 1) age 35-90, 2) right handed, 3) English dominant language.

Exclusion criteria: contraindications for MRI (e.g. metal implants, pregnancy), history of head injury sufficient to warrant medical attention, history of alcohol or substance abuse or dependence, history of major psychiatric illness requiring treatment, history of cancer or other neoplastic syndromes, history of major neurologic illness (e.g. epilepsy).

Procedures.

Crossover Design. This study will be conducted using a crossover design in which each participant will complete two visits spaced two weeks apart. At one visit, they will receive LIFUP sonication to the right amygdala, and at the other, they will receive sonication to the left entorhinal cortex. The order of conditions will be randomized and counterbalanced across participants. Participants will be blinded to condition order, and all other testing will be conducted the same at both visits.

Screening. Participants who have consented to be contacted regarding future research projects will be contacted by study staff who will conduct a telephone screening to ensure eligibility.

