fMRI and LIFUP administration. Prior to receiving LIFUP sonication, the LIFUP transducer will be aimed at the appropriate target region for the visit (either the amygdala or the entorhinal cortex) and gently strapped in place to their head. Participants will then return to the scanner where a T1 image will verify the position of the LIFUP transducer and allow for estimation of the spatial location of the sonication beam focus. If needed, adjustments to transducer placement will be made to ensure that the beam focus is correctly aimed; an additional T1 will be collected after adjustment. Once correct placement of the transducer has been confirmed, LIFUP will be administered in 10 sonifications at 650kHz, 720mW/cm, duty cycle 5% duration 30s, with 30s spacing between sonifications. LIFUP will be administered with a pulse repetition frequency of 10Hz for amygdala sonication and 100Hz for entorhinal cortex sonication. BOLD fMRI will be collected simultaneously during LIFUP administration.

MRI Data Acquisition. We will use a 3-Tesla Siemens PRISMA scanner. We will collect T1, T2, hi-res hippocampal T2, and diffusion-weighted structural images for each participant.

Additionally, we will collect arterial spin labeling and BOLD fMRI both before and after LIFUP, as well as BOLD fMRI during LIFUP administration. We will be using Human Connectome Project scan sequences to collect these images; detailed information about the protocols can be obtained here: <http://www.humanconnectome.org/documentation/Q1/imaging-protocols.html>.

Behavioral Testing. Participants will be administered the behavioral tests described below twice at each of their in-person sessions; once before LIFUP and once after LIFUP.

Verbal Free Recall Task. Verbal memory will be assessed using the Rey Auditory Verbal Learning Test (RAVLT) which involves repeated presentation of a list of 15 words. The order of RAVLT form administration will be randomized and counterbalanced across participants.

Spatial Navigation Memory Task. Participants will be presented with a computerized spatial arena simulating a museum art gallery. They will be instructed to learn the locations of three objects placed throughout the gallery. After the Learning Phase, the subjects will then be asked to locate the objects' shown location sans stimuli immediately after learning the set of locations of each object. After each learning phase, participants will complete an unrelated Distractor Task

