RS-fMRI. We will compare the functional connectivity of the brain at rest before and after stimulation. Independent component analyses (ICA) will be used to statistically extract functional networks from each participant's rs-fMRI. Dual-regression analysis will then compare resting state networks between baseline and post-LIFUP to determine the effect of LIFUP on resting state functional connectivity. Age, sex and education will be included as additional regressors. Dual regression will also assess the association between these LIFUP-related longitudinal resting state network changes and emotional reactivity and memory performance.

Arterial Spin Labeling. Pulsed Arterial Spin Labeling (PASL) scans produce a perfusion image with voxel values representing local perfusion rates. For each subject, will be collected both before and after LIFUP. These PASL images will then be linearly registered to each subject's T1 structural image. Perfusion images will be processed by using the BASIL (Chappell et al., 2008) toolbox, including partial volume correction, then transferred to MNI space using non-linear registration in FSL. Then, a comparison of pre-vs-post tFUS sonication perfusion in the amygdala and entorhinal cortex will be conducted individually for each subject by subtracting the registered pre- sonication perfusion map from the post-sonication perfusion map. A 2×2 repeated measures analysis of variance (ANOVA), corrected for multiple comparisons using False Discovery Rate (FDR), will then be used to compare the longitudinal perfusion changes between amygdala sonication and ErC sonication.

Hypothesis 2. LIFUP of the amygdala will result in reduced subjective emotional reactivity to emotionally-salient stimuli compared to those presented before LIFUP; this reduction will not be observed with entorhinal cortex LIFUP.

Behavioral Analysis. Subjects, who will be unaware of the exact timing of the sonication onset, will be asked to report any unusual feelings, sensations or distress. To determine the effect of LIFUP on emotional reactivity, analyses of variance (ANOVA) will compare subjective valence

and arousal ratings between pre-LIFUP and post-LIFUP administrations of the IAPS task. Additionally, state and trait anxiety scores will be compared pre and post-LIFUP to determine LIFUP-related changes in anxiety levels.

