Physiological Analysis. To determine the effect of LIFUP on psychophysiological reactivity to emotionally-salient stimuli, interbeat intervals (IBIs) will be calculated for each stimulus presentation using Autonomic Nervous System Laboratory (ANSLab). These IBIs in response to stimuli will be analyzed using multilevel modeling with a repeated measures within-subjects design, with target (amygdala / entorhinal cortex), timepoint (pre / post LIFUP), and instructions (view, watch, reappraise) included as model factors.

Hypothesis 3. LIFUP of the entorhinal cortex will result in better performance on memory tasks compared to both amygdala LIFUP and pre-LIFUP conditions.

Behavioral Analysis. To determine the effect of LIFUP stimulation on memory performance, performance on memory assessments before LIFUP, after entorhinal cortex LIFUP, and after amygdala LIFUP will be compared using ANOVA.

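### Comparing perfusion between targets as raw post-minus-pre change fixes the weight of the pre-LIFUP scan at 1; this is unbiased, but usually less precise than adjusting for that scan.

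*Combined protocol and SAP*

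**What the plan says.** All references are to the combined protocol and SAP.

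- **Participants and Crossover Design:** "Participants will consist of 21 adults aged 35-90", and "each participant will complete two visits spaced two weeks apart", one visit per target. On allocation: "The order of conditions will be randomized and counterbalanced across participants". No power, effect size or standard deviation is given.
- **MRI Data Acquisition:** "we will collect arterial spin labeling and BOLD fMRI both before and after LIFUP". Each visit therefore has its own baseline perfusion scan.
- **Arterial Spin Labeling:** the pre/post comparison is made for each participant "by subtracting the registered pre- sonication perfusion map from the post-sonication perfusion map". A 2×2 repeated-measures ANOVA with FDR correction "will then be used to compare the longitudinal perfusion changes between amygdala sonication and ErC sonication". The two factors are not named, and no baseline or period term is mentioned. Covariates are named in the neighbouring RS-fMRI section, but they are age, sex and education and apply to that analysis only.
- **Hypotheses 1a and 1b:** each predicts that perfusion rises in the sonicated region and does not do so after sonication of the other target.

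**The concern.** The 2×2 could be target by time on raw perfusion, or target by region on the change maps. On either reading, the comparison of targets is a difference between two post-minus-pre changes, so the pre scan enters with a weight of exactly 1.

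In a crossover, a person's stable perfusion level already cancels when the two visits are compared. The pre scan then helps only through variation that is specific to a visit and shared by its two scans. If that shared part is modest, subtracting the whole pre value adds more noise than it removes.

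What is at stake is precision in a study of 21 people whose size is not justified by any calculation. The information needed to do better is already being collected.

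**Working it through.** **Inputs.** From the documents: n = 21, two visits per person, a pre and a post perfusion value at each visit, and randomized order. Not in the documents, so assumed: equal variance s² for every perfusion value, within-visit pre/post correlation r1, correlation r2 between any two values from different visits, no dropout, two-sided alpha 0.05. The plan has no power or precision figure to reproduce.

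**Step 1: the two contrasts.** For each participant let X = pre (amygdala visit) − pre (entorhinal visit) and Y = post (amygdala visit) − post (entorhinal visit). Then:

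- Var(X) = Var(Y) = 2s²(1 − r2), and Cov(X, Y) = 2s²(r1 − r2).
- The correlation of X and Y is p = (r1 − r2)/(1 − r2).
- Planned contrast, Y − X: variance 4s²(1 − r2)(1 − p) = 4s²(1 − r1) per person.
- Adjusted contrast, known slope: variance 2s²(1 − r2)(1 − p²) per person.
- Large-sample ratio, adjusted to planned: (1 − p²)/[2(1 − p)] = (1 + p)/2.

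**Step 2: the cost of estimating the slope.** This multiplies the ratio by 1 + 1/(n − 3) = 19/18 at n = 21, or by 1 + 1/(n − 4) = 18/17 if an order term is also fitted.

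**Step 3: results.** Equivalent N is 21 divided by the ratio, that is, the number of participants the planned method would need for the same variance. The last column is the power of the adjusted test (no order term, 19 df) if the planned test (20 df) had 80% power, which corresponds to a standardized paired effect of 0.643.

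| p | Ratio, ×19/18 | Equivalent N | Ratio with order term, ×18/17 | Power |
|---|---|---|---|---|
| 0 | 0.53 | 39.8 | 0.53 | 97% |
| 0.3 | 0.69 | 30.6 | 0.69 | 92% |
| 0.5 | 0.79 | 26.5 | 0.79 | 88% |
| 0.7 | 0.90 | 23.4 | 0.90 | 84% |
| 0.8 | 0.95 | 22.1 | 0.95 | 82% |
| 0.9 | 1.003 | 20.9 | 1.006 | 79.7% |
| 1 (limit) | 1.06 | 19.9 | 1.06 | 77.6% |

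Simulation of 100,000 trials of 21 participants at each of p = 0, 0.3, 0.5, 0.7, 0.8, 0.9 and 0.95 gave ratios within 0.005 of the ×19/18 formula.

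**Step 4: break-even.** Setting (1 + p)/2 × 19/18 = 1 gives p = 36/19 − 1 = 0.895. With the order term, p = 34/18 − 1 = 0.889.

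**Step 5: what p means.** It is not the ordinary pre/post correlation. With r1 = 0.9 and r2 = 0.7, p = 0.2/0.3 = 0.67 (equivalent N 23.9). With r1 = 0.9 and r2 = 0.5, p = 0.4/0.5 = 0.80 (equivalent N 22.1). Since r1 = r2 + p(1 − r2), reaching p = 0.895 when r2 = 0.6 needs r1 = 0.6 + 0.895 × 0.4 = 0.96.

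**The case against.** **The size is unknown.** This stands. Nothing in the documents fixes p, and at p of 0.8 or more the gain is about one participant or none. The top of the table needs two scans in one visit to agree no better than scans two weeks apart.

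**A reader might infer that adjustment is always at least as precise.** That is true only in large samples or with a known slope. With 21 participants it fails above p of about 0.89, though the loss is small.

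**A reader might infer that the planned analysis is biased.** The documents do not support this: order is randomized and counterbalanced, so both estimators target the same between-target effect.

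**Subtraction has its own advantage.** Suppose a visit-1 effect persisted and shifted the visit-2 pre and post scans equally. Subtraction would remove it. Adjustment with slope b would leave (1 − b)(cE − cA)/2 in the target effect, where cA and cE are the effects carried over from amygdala and entorhinal sonication. The documents do not show that such an effect exists, but this is a sound reason to keep the change-score result alongside.

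**A reader might infer that Hypotheses 1a and 1b rest wholly on the between-target contrast.** They do not. Each also states an increase within the sonicated target, which the adjusted intercept does not test and the change maps do.

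**A reader might extend the point to interbeat intervals.** Physiological Analysis specifies a multilevel model of responses to individual stimuli, "with target (amygdala / entorhinal cortex), timepoint (pre / post LIFUP), and instructions (view, watch, reappraise) included as model factors". It subtracts no baseline summary, its random effects are not stated, and the calculation above does not cover it.

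**Conclusion.** The point holds as a matter of efficiency, for the between-target perfusion contrast only. The plan fixes the baseline weight at 1 where it could be estimated from scans already collected. At n = 21 the adjusted contrast has about 0.69 to 0.84 of the planned variance for p from 0.3 to 0.6, which is worth roughly 10 down to 4 extra participants. The advantage shrinks to about one participant at p = 0.8, disappears near 0.89, and becomes at worst a loss of about 5.6% of variance (5.9% with an order term), or about one participant.

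The position of each value on this scale depends on the assumed p, equal pre and post variances and complete data. The cap on the loss does not need equal variances. If k is the ratio of the pre to the post standard deviation of the between-visit differences, the planned variance is proportional to 1 + k² − 2pk = (1 − p²) + (k − p)². This is never below the adjusted 1 − p², so only the slope-estimation factor can make adjustment worse.

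**What to change.** State the following in Arterial Spin Labeling.

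1. Name the two factors of the 2×2, and say whether the analysis is by region or by voxel.
2. For the between-target contrast, regress the between-visit difference in post-LIFUP perfusion (amygdala visit minus entorhinal visit) on the between-visit difference in pre-LIFUP perfusion, per region or per voxel, with a centred order (period) term. Test the intercept as the target effect and keep the planned FDR correction. Code order symmetrically about zero (+½ and −½), because 21 people cannot split evenly between two orders and the intercept should weight both orders equally.
3. Keep the post-minus-pre analysis for the within-target increases in Hypotheses 1a and 1b, and as a sensitivity analysis for the between-target contrast. It also guards against a visit-1 effect that persists into the visit-2 baseline.

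The cost is one degree of freedom for the baseline, one more for order, and a possible small loss if p exceeds about 0.89. No new data are needed. By region this is a short addition to the text; by voxel, each voxel needs its own baseline covariate, which takes more work to set up.

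### The ratings analysis for Hypothesis 2 states only a pre-versus-post comparison, not the target-by-timepoint contrast that the hypothesis needs

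*Combined protocol and SAP*

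**What the plan says.** Hypothesis 2 in the Data Analysis Plan has two clauses. The first is that "LIFUP of the amygdala will result in reduced subjective emotional reactivity to emotionally-salient stimuli compared to those presented before LIFUP". The second is that "this reduction will not be observed with entorhinal cortex LIFUP".

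The Behavioral Analysis paragraph below it gives the ratings analysis in one sentence: ANOVA will compare subjective valence "and arousal ratings between pre-LIFUP and post-LIFUP administrations of the IAPS task". No factors are listed. The following sentence treats state and trait anxiety in the same way, before against after LIFUP.

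For other outcomes the plan names the targets:

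- Arterial Spin Labeling: a repeated measures ANOVA will "compare the longitudinal perfusion changes between amygdala sonication and ErC sonication".
- Hypothesis 2, Physiological Analysis: interbeat intervals go into a multilevel model "with target (amygdala / entorhinal cortex), timepoint (pre / post LIFUP), and instructions (view, watch, reappraise) included as model factors".
- Hypothesis 3, Behavioral Analysis: "performance on memory assessments before LIFUP, after entorhinal cortex LIFUP, and after amygdala LIFUP will be compared using ANOVA".

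On design, the Crossover Design section gives each participant both targets, at visits two weeks apart. It adds: "The order of conditions will be randomized and counterbalanced across participants". Under Behavioral Testing, the tests are given "twice at each of their in-person sessions; once before LIFUP and once after LIFUP".

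**The concern.** The second clause of Hypothesis 2 is a statement about a difference between targets. A pre-versus-post comparison, taken alone, does not address it.

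The first clause is also exposed. At every visit the post-LIFUP ratings come from the second run of a 96-trial task (24 VIEW + 24 WATCH + 48 REAPPRAISE), of which 24 + 48 = 72 trials show negative pictures. If participants habituate to negative pictures, ratings fall in the direction the hypothesis predicts, whatever was sonicated. The negative-minus-neutral score defined under the International Affective Picture Stimuli Task removes drift shared by both picture types, but not habituation specific to negative pictures.

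The stated sentence can be carried out in ways that mislead. With a separate test per target, a decline common to both visits can by chance reach significance at the amygdala visit only, and so look like Hypothesis 2. With pre and post pooled over targets, the same decline reads as a LIFUP effect. The crossover already supplies the comparison that cancels a common decline, but the plan does not state it for the ratings.

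**Working it through.** **What each comparison estimates.** Score change as a fall. Let *h* be the decline on repeat testing, common to both visits, and let *a* and *e* be the falls caused by amygdala and entorhinal sonication.

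- Amygdala visit, pre minus post: *h* + *a*
- Entorhinal visit, pre minus post: *h* + *e*
- Pooled over targets: *h* + (*a* + *e*)/2
- Target-by-timepoint contrast: (*h* + *a*) − (*h* + *e*) = *a* − *e*

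Only the contrast is free of *h*.

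**Inputs.** The document gives n = 21 and the crossover. It gives no alpha, SD, effect size or size of decline for this analysis, so there is no planned figure to reproduce. Assumed: two-sided 0.05; change-score SD of 1 at each visit; correlation *r* between the two changes of 0 or 0.5; *a* = *e* = 0; *h* = 0.3, 0.5 or 0.8 SD; sequences split 11/10. Simulated values use 200,000 runs per case.

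**Single-target paired test.** Noncentral t with 20 df and noncentrality *h*√21 = 1.37, 2.29, 3.67. Rejection probability: 0.258, 0.587, 0.936.

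**Amygdala significant, entorhinal not.** If the changes are independent this is p(1 − p): 0.258 × 0.742 = 0.191; 0.587 × 0.413 = 0.242; 0.936 × 0.064 = 0.060. Simulation agrees (0.190, 0.242, 0.059).

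**Pooled over targets.** The mean of the two changes has SD √((1 + *r*)/2), so the standardised effect is *h*/√((1 + *r*)/2). For *h* = 0.3 this is 0.424 at *r* = 0 and 0.346 at *r* = 0.5.

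| No LIFUP effect; *h* = 0.3 / 0.5 / 0.8 | *r* = 0 | *r* = 0.5 |
|---|---|---|
| Amygdala significant, entorhinal not | 19 / 24 / 6% | 14 / 17 / 5% |
| Pooled pre/post rejects | 46 / 87 / 100% | 33 / 71 / 98% |
| Order-adjusted contrast, two-sided | about 5% | about 5% |
| Contrast in predicted direction and significant amygdala fall | 2.2 / 2.4 / 2.5% | 1.8 / 2.3 / 2.5% |

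With no decline at all, the first row is about 2%. If the decline is 0.3 SD smaller at the second visit, the order-adjusted contrast still rejects in 4.8 to 5.0% of trials, and the two-part rule is met in at most 2.5%.

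**Why the contrast alone is not enough.** *a* − *e* is also positive when nothing happens at the amygdala visit and ratings rise at the entorhinal visit. With no amygdala fall and an entorhinal rise of 0.5 / 0.8 SD, the contrast is significant in 34 / 69% of trials (*r* = 0) or about 58 / 94% (*r* = 0.5). Requiring a significant amygdala fall as well brings this to about 2.5%.

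**Power cost.** The contrast has SD √(2(1 − *r*)), which is 1.414 at *r* = 0 and 1 at *r* = 0.5. With 19 df, 80% power needs 0.645 SD of the difference: 0.645 × 1.414 = 0.91 change-SD at *r* = 0, or 0.645 at *r* = 0.5. If the entorhinal change is zero, the two-part rule reaches 80% power at an amygdala fall of about 0.92 (*r* = 0) or 0.72 (*r* = 0.5). A single amygdala pre/post test reaches it at about 0.64. At a true fall of 0.5 SD the rule is met in 30% or 42% of trials, against 59% for the single test.

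**The case against.** The strongest reply is that this is brevity, not a wrong analysis. The sentence lists no factors, so it does not exclude target. The hypothesis directly above it names both targets, target is the crossover factor, and the next paragraph under the same hypothesis lists target and timepoint. A sympathetic reader could take the ratings ANOVA as the same within-person layout in shorthand, and in that case none of the misleading percentages would apply.

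That reading is possible, but the text does not establish it. The model in the next paragraph is for interbeat intervals, whereas Hypothesis 2 is about subjective reactivity. Even that model does not name the target-by-timepoint interaction as the test. An analyst could follow the ratings sentence with separate tests, a pooled test or an interaction model, and reach different conclusions.

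Four further points stand in part:

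- The percentages depend on an assumed decline and on how an unspecified ANOVA is run. The documents give no evidence on how much habituation to expect.
- The ratings sentence does not name the negative-minus-neutral score, but the task description defines emotional reactivity that way, so the score is reasonably implied. Naming it is a clarification only.
- The two-part rule costs power, and a sponsor might prefer the contrast alone. The rule does, however, follow the two clauses of the hypothesis.
- The contrast compares two active sonications, which also differ in pulse repetition frequency (10 Hz and 100 Hz, fMRI and LIFUP administration). That limits what any analysis can show; it does not favour the pre/post comparison.

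**Conclusion.** The concern holds, and the plan should be changed. The only stated analysis of subjective ratings does not include the comparison that the second clause of Hypothesis 2 asserts, and as written it cannot tell a LIFUP effect from change on repeat testing. This is clear from the text and needs no assumed numbers.

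The size of the risk does rest on assumptions. For common declines between 0.3 and 0.8 SD and no LIFUP effect, the false Hypothesis 2 pattern appears in roughly 5 to 24% of trials with separate tests, and a pooled test rejects in 33 to 100%. If the investigators already intend to test the target-by-timepoint interaction, the change only puts that intention on record.

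The finding is limited to the ratings, with anxiety as a secondary instance. It does not say that the plan never compares targets.

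**What to change.** State the ratings analysis as follows:

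- **Model.** Analyse each participant's negative-minus-neutral valence and arousal scores (WATCH minus VIEW, if that is what N-S denotes) with target, timepoint and their interaction, adjusted for visit order.
- **Criterion for Hypothesis 2.** Require both a significant target-by-timepoint contrast in the predicted direction and a significant pre-to-post fall at the amygdala visit. Report this separately for valence and arousal, and say in advance whether one or both must meet it.
- **Entorhinal visit.** Report the change with its confidence interval. Do not read a non-significant result as no change.
- **Anxiety.** Apply the same contrast to state anxiety as a supporting analysis, since Hypothesis 2 does not mention anxiety.

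The change needs wording only and no new data. Its price is the loss of power shown above, which matters with 21 participants and should be acknowledged in the plan.

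One limit should also be stated. A common decline of 0.5 SD that entorhinal sonication cancels by raising ratings (*h* = 0.5, *a* = 0, *e* = −0.5) gives the same data as a true amygdala fall of 0.5 SD, and meets the rule equally often (30% or 42%). Without a no-sonication visit, no analysis of these data can tell the two apart.

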within the task but unrelated to the Mission. The navigation and distractor task paradigm will be repeated three times. During the fourth and final trial, retrieval of spatial information during this trial will be measured as the distance between the location that participants selected and the true location of the object. Shorter distances will indicate better spatial memory performance. This assessment has four forms, the order of which will be randomized and counterbalanced across participants.

Brief Visuospatial Memory Test. In this test, the participant is presented with a 2x3 array of geometric figures for 10 seconds, then instructed to draw the figures from memory in the correct location on the page. The task consists of three learning trials, one long delayed recall trial, and one recognition trial. Learning performance will be calculated as the proportion of presented figures and figure locations successfully recalled during the initial presentations of the six-figure array. Long delayed recall memory performance will be calculated as the proportion of presented figures and figure locations successfully recalled freely after a 20-minute delay. Memory retention will be calculated as the proportion of presented figures successfully identified during a forced-choice recognition task. This assessment has 4 forms that will be used for repeat testing, the order of which will be randomized and counterbalanced across participants.

State Trait Anxiety Inventory. This is a questionnaire used to measure anxiety-like symptoms. The first half of the questionnaire asks about the degree to which several listed statements align with how a participant feel at the current moment (state anxiety). The second half asks about the degree to which the listed statements align with how a participant typically feels (trait anxiety).

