International Affective Picture Stimuli Task. In this task, participants complete multiple trials in which a 15-second fixation cross is followed by a 2-second color-coded instruction for one of three trial types: WATCH (passively view a negative image), VIEW (passively view a neutral image), or REAPPRAISE (actively reappraise a negative image). The instruction image is followed by a 5 second presentation of a negatively or neutrally-valenced image. After each image presentation, participants rate their subjective level of current arousal and the degree of awfulness of the image (valence). The task consists of 24 VIEW trials, 24 WATCH trials, and 48 REAPPRAISE trials. Objective reactivity to each stimulus will be measured using galvanic skin response and heart rate. Emotional reactivity in this task will be quantified using the difference between negative and neutral stimuli (N-S). Emotional reappraisal will be quantified by taking the difference of the negative reappraisal stimuli and the negative stimuli (NR - N).

Data Analysis Plan.

Hypothesis 1a. LIFUP of the amygdala will decrease BOLD activation in the amygdala and functionally associated regions (e.g. DLPFC), as well as functional connectivity between the amygdala and connected regions. It will also increase perfusion in the amygdala. These changes will not be observed in response to LIFUP of the entorhinal cortex.

Hypothesis 1b. LIFUP of the entorhinal cortex will increase BOLD activation in the entorhinal cortex and functionally associated regions (e.g. DLPFC), as well as functional connectivity between the entorhinal cortex and connected regions. It will also increase perfusion in the entorhinal cortex. These changes will not be observed in response to LIFUP of the amygdala.

MRI Analysis. Analyses will be performed using FSL Version 5.0 (www.fmrib.ox.ac.uk/fsl). Stimulation-related functional data processing will include motion correction to the mean image, spatial smoothing (Gaussian Kernel FWHM = 8mm), high-pass temporal filtering ($t > 0.01$ Hz) and regression-based removal of outliers. Processing of rs-fMRI will include correcting for

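### The anxiety comparison reads a pre/post difference as LIFUP-related without naming target; with two active targets and no sham, it cannot be separated from ordinary within-visit change (minor)

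*Combined protocol and SAP*

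**What the plan says.** The Behavioral Analysis paragraph under Hypothesis 2 closes with the only anxiety analysis in the document: "state and trait anxiety scores will be compared pre and post-LIFUP to determine LIFUP-related changes in anxiety levels". It names no target factor, no comparison between visits and no statistical test.

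The Crossover Design paragraph gives right amygdala sonication at one visit "and at the other, they will receive sonication to the left entorhinal cortex". No sham or no-stimulation visit is described. Under Behavioral Testing, the tests are given "twice at each of their in-person sessions; once before LIFUP and once after LIFUP", so each participant supplies four anxiety scores.

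Two other analyses do use target. The interbeat-interval model under Physiological Analysis is specified "with target (amygdala / entorhinal cortex), timepoint (pre / post LIFUP") and instruction. The Arterial Spin Labeling paragraph compares perfusion change between the two sonication sites.

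**The concern.** A pre/post difference measures LIFUP only if nothing else moves the score between the two administrations, or if a control removes what does. Here the only available control is the same participant's change at the other target, and the anxiety sentence does not call on it.

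Other influences are plausible. Between administrations the transducer is "gently strapped in place to their head" and the participant is scanned. The questionnaire is repeated. The picture task is also given before and after: "The task consists of 24 VIEW trials, 24 WATCH trials, and 48 REAPPRAISE trials", so 24 + 48 = 72 of 96 trials show negative images. These could push anxiety up or down. The trait half asks about statements that "align with how a participant typically feels (trait anxiety"), so a shift in it within one visit is more plausibly a retest effect than a LIFUP effect.

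Randomised, counterbalanced order does not solve this. It balances visit effects between targets but does not remove a pre-to-post shift that occurs at both visits. The risk is that an ordinary within-visit change is reported as caused by LIFUP. If the visits were also pooled, an effect at one target only would be estimated at half its size.

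**Working it through.** The plan states no alpha, SD, effect size or sample-size calculation for anxiety, so there is no figure to reproduce.

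**Input from the document.** n = 21 ("Participants will consist of 21 adults aged 35-90"), each measured pre and post at two visits.

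**Assumptions, not in the document.** Two-sided 5% tests; within-visit changes D_A (amygdala) and D_E (entorhinal), each with SD 1; correlation rho between them from −0.3 to 0.5; no LIFUP effect; a change d common to both visits; an 11/10 split by order.

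**Three tests.**

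- One visit alone: SE = 1/√21 = 0.218, df 20. For d = 0.3 the noncentrality is 0.3/0.218 = 1.375, giving 25.8% significant.
- Pooled mean (D_A + D_E)/2: SE = √[((1 + rho)/2)/21], df 20. At rho 0 this is √(0.5/21) = 0.154; for d = 0.3 the noncentrality is 1.94, giving 45.7%.
- Target contrast adjusted for visit number: half the difference between the two order groups in (visit-1 change − visit-2 change). SE = √[2(1 − rho)(1/11 + 1/10)/4], df 19; at rho 0 this is 0.309. Its expected value is d − d = 0 for any common change.

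**Chance of a significant result with no LIFUP effect (noncentral t; contrast by simulation).**

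| Common change | Test | rho −0.3 | rho 0 | rho 0.3 | rho 0.5 |
|---|---|---|---|---|---|
| 0.3 SD | Pooled | 60% | 46% | 37% | 33% |
| 0.3 SD | One visit | 26% | 26% | 26% | 26% |
| 0.5 SD | Pooled | 96% | 87% | 77% | 71% |
| 0.5 SD | One visit | 59% | 59% | 59% | 59% |
| Either | Target contrast | 5% | 5% | 5% | 5% |

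The contrast also held 5% when an extra 0.5 SD change was added at visit 1.

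**Visits tested separately.** Significance at both visits would argue against target specificity; only significance at exactly one would falsely suggest it. P(exactly one) = 2 × [P(at least one) − P(a given visit)]. For a common 0.5 SD change:

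- rho 0: 2 × (0.829 − 0.587) = 0.484, about 48%. Both visits: 0.829 − 0.484 = 0.345.
- rho 0.5: 2 × (0.756 − 0.587) = 0.338. A second simulation gives 2 × (0.751 − 0.585) = 0.332, so about a third. Both visits: 0.756 − 0.338 = 0.418.

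**Power.** The contrast reaches 80% at a target difference of 1.04 SD (rho −0.3), 0.91 (0), 0.76 (0.3) or 0.65 (0.5). For an amygdala-only effect of 0.8 SD it has 58%, 69%, 84% and 94% power in that order. The pooled test, which then sees 0.8/2 = 0.4 SD, has 84%, 69%, 58% and 52%.

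**The case against.** The best reply is that the sentence is under-specified, not wrong. It does not say that target will be ignored, and the plan uses target for perfusion and interbeat intervals. Hypothesis 2, which heads the paragraph, is target-specific. Much of this stands. A reader might infer that the sponsor chose to pool the visits, but the document neither says so nor rules it out; the valence and arousal ratings and the resting-state comparison are also worded as pre/post. However, Hypothesis 2's target clause concerns emotional reactivity, and nothing elsewhere supplies a target contrast for anxiety. The one contrast named does not support the interpretation attached to it.

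Second, if visits are tested separately, a common change tends to show at both targets and so counts against specificity. That stands, and it is why the exactly-one figures are the relevant ones for a false claim of specificity. It does not rescue the reading of either pre/post result as LIFUP-related.

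Third, a target contrast asks a narrower question. A change at both visits could be a real effect of both targets, and the contrast is blind to it. That also stands, but the pre/post test cannot identify such an effect either; only a sham could.

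Fourth, a reader might infer that the documents show anxiety drifting within a visit. They describe procedures, not effects on anxiety, and do not state where the questionnaire falls relative to the picture task. The sources of drift are plausible but undocumented, and the direction is open.

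**Conclusion.** The point holds as a minor one. As worded, the anxiety comparison cannot separate a LIFUP effect from ordinary within-visit change, whether visits are pooled or taken singly. That follows from the design and does not depend on the assumed values. The size does: the percentages rest on an assumed drift, a unit SD and rho between −0.3 and 0.5, and illustrate the exposure rather than predict it.

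Severity is limited because anxiety is introduced as an additional comparison with no hypothesis of its own. A reader might go further and conclude that the test of Hypothesis 2 is invalid. The documents do not support that on the strength of this sentence, since that hypothesis concerns emotional reactivity and not anxiety.

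**What to change.** Replace the anxiety sentence with:

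*For each visit, the post-minus-pre change in state anxiety will be analysed in a linear model with target, visit number and participant as fixed factors. The target estimate, with its 95% confidence interval, is the test of a target-specific LIFUP effect. Mean pre/post changes within each target will be reported with 95% confidence intervals as descriptive and uncontrolled. Trait anxiety will be analysed in the same way as a supportive measure.*

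Visit number belongs in the model because 21 participants cannot split evenly by order. An extra 0.5 SD change at visit 1 would otherwise shift the estimate by 0.5/21 = 0.024 SD.

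A mixed model on the four scores is not a safe substitute. With participant and visit intercepts only, the simulated error rate runs from 0.7% (rho 0.5) to 8.4% (rho −0.3). Adding a random participant-by-timepoint term does not cure the negative end: its variance cannot go below zero, so it cannot represent negative correlation, and the error rate stays at about 8% to 9% at rho −0.3.

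The cost is one changed sentence, with no new visits, instruments or data. The change is not made for power, which is modest at n = 21 and, at negative rho, lower than that of the pooled test for a one-target effect. A participant with only one completed visit adds nothing to the contrast. An effect common to both targets remains beyond this design without a sham.
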